#### **1.4.2 Specific objective**

- (1) Evaluate the effects of static balance training, dynamic balance training, and combined static-dynamic balance training on the stability of beginner gymnasts. Quantify the maximum single-leg extension distance (reflecting lower limb support force) and the bilateral symmetry index (reflecting neuromuscular coordination) through the SEBT test to compare the differential effects of different training modes on stability improvement.
- (2) To evaluate the effects of static balance training, dynamic balance training, and combined static-dynamic balance training on the jumping skills of beginner gymnasts, this study measures the changes in data (such as jumping height, peak force, rate of force development, and impulse) of athletes during countermovement jump (CMJ) and single-leg countermovement jump (SLCMJ) before and after training. Through these measurements, it

aims to deeply analyze the mechanism of action of different training modes in enhancing the jumping ability of beginner gymnasts.

(3) This study aims to explore the improvement effects of static balance training, dynamic balance training, and combined static-dynamic balance training on the performance of gymnastic movements (such as standing 360° single-leg turn and straight jump 360° turn). Through three-dimensional motion capture technology, the study assesses beginner gymnasts in terms of center of gravity deviation distance, body oscillation amplitude, rotation smoothness index, and landing impact force during the standing 360° single-leg turn. For the straight jump 360° turn, it conducts quantitative analysis based on center of gravity deviation distance, joint angle variation, vertical jump efficiency, and landing impact force.

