#### **3.5.2 Exclusion Criteria**

1. Participants suffering from acute or chronic musculoskeletal injuries (lasting for 6 months or more), neurological disorders (such as epilepsy), or vestibular dysfunction.
2. Ranked athletes or elite athletes.
3. Participants with poor compliance (< 80%) who are unable to complete the 8 - week exercise intervention program.
4. Individuals who have recently undergone or are scheduled to undergo surgery within three months.

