### **3.6 Sample Size Estimation**

Using G - power 3.1 (Figure 10), the study focuses on time (within - subject factor), group (between - subject factor), and their interaction effects. The effect size is set to medium (0.35), with an alpha value of 0.05 and a statistical power of 0.80. A total of four groups will be included (static balance, dynamic balance, combined static and dynamic balance, and a control group), with measurements conducted twice, pre - and post - intervention. The calculated sample size is 52 participants. Considering a dropout rate of 15%, 60 participants will be recruited. Participants will be randomly assigned to four groups, with 15 participants in each group. Since the total dropout rate applies uniformly and participants are equally distributed across the four groups, each group's dropout rate is also 15%.

[figure not shown]

Figure 10 Flow chart of the G-power

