### **3.8 INTERVENTION METHODS**

Participants in the SG intervention group will complete an 8-week training program consisting of Plank Support, Single-Leg Stance, Eyes-Closed Double-Leg Stance, and Half-Squat Exercise. The DG intervention group will engage in Landing Control Training, Balance Beam Walking, jumping onto the Balance Beam, and Squat-to-Stand Exercises. The SDG intervention group will perform Plank Support, Single-Leg Stance, Eyes-Closed Double-Leg Stance, Half-Squat Exercise, Landing Control Training, Balance Beam Walking, jumping onto the Balance Beam, and Squat-to-Stand Exercises. Each exercise will be repeated 3 times or the corresponding number of times per session, with each session lasting 15 minutes (including 30 minutes of dynamic and static balance exercises), conducted twice a week for 8 weeks. All participants will enroll simultaneously, and each group will be guided by qualified instructors. Before and after each training session, participants will wear a heart rate monitor (Xiaomi Smart Band) on their wrist to ensure adherence to the prescribed training intensity outlined in Tables 13, 14, and 15. Additionally, participants may adjust their limb positions and movement intensity based on their physical condition. At the end of each session, training logs will be completed to document the activities. Only data from participants who adhere to at least 80% of the prescribed training program will be included in the analysis.

Participants in the control group (CG) will continue their regular training routine as detailed in Tables 7 and 8. They will be advised to maintain their usual daily activities without incorporating any additional exercises.

Table 13: Static balance training intervention content (n=15)

Week	content	Minutes/ Groups	Inter-group Rest Duration	Training duration	HR Monitoring Indicators	Heart Rate Monitoring Equipment	Intervention time	Heart rate range	Equipment
W 1	baseline test								
W 2-3	①Double leg stand ②Single leg stand	1/3	Rest for 2 minutes	15minutes	Resting Heart Rate (Before Training)/Maxi mum Heart Rate/Maximum Heart Rate	Xiaomi Smart Band	8 weeks, 2 times per week, 15 minutes each time	80bpm-100bpm	Balance board、BOSU ball
W 4	①Eyes-closed double-leg stance ②Plank support	1/3	Rest for 2 minutes	15minutes				80bpm-110bpm	Balance board 、 BOSU ball、 Gymnastic mat

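### Section 3.6: recruiting 60 with the stated 15% dropout leaves 51 participants, one short of the 52 said to be required; the effect on power is small

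*Protocol*

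**What the plan says.** Section 3.6 of the protocol gives the whole chain from inputs to recruitment target. The design has four groups and two measurements, and "the study focuses on time (within - subject factor), group (between - subject factor), and their interaction effects". The inputs are given as: "The effect size is set to medium (0.35), with an alpha value of 0.05 and a statistical power of 0.80". The result and the allowance for losses follow: "The calculated sample size is 52 participants. Considering a dropout rate of 15%, 60 participants will be recruited". Allocation is equal: "Participants will be randomly assigned to four groups, with 15 participants in each group". The paragraph closes by carrying the loss rate down to group level, saying that each group's "dropout rate is also 15" per cent.

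Section 3.6 prints neither the formula that turns 52 into 60 nor the pre-post correlation. Figure 10, which shows the G*Power step, is not reproduced in the text available, so the correlation and the test chosen may be stated there.

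**The concern.** An allowance for dropout should leave the required number after the assumed losses. Here the protocol fixes the required number, the loss rate, the recruitment target and the group size, and the last two do not return the first. The discrepancy can be seen from the one paragraph, and the missing figure cannot remove it, because Figure 10 concerns how 52 was reached and not what 15% of 60 is.

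At stake is whether the stated size and power match what the trial should expect to analyse. The number 52 is the protocol's only justification for its size, so a reader will take it as the expected analysed number.

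**Working it through.** **Inputs, all from section 3.6:** effect size f = 0.35 (read as Cohen's f), alpha 0.05, power 0.80, k = 4 groups, m = 2 measurements, required N = 52, dropout 15% overall and per group, recruited 60, 15 per group. The pre-post correlation ρ is not given in the text, so any value used below is an assumption.

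**Step 1. Reproduce 52.** For the group-by-time interaction under the G*Power default convention, λ = f² · N · m / (1 − ρ), with 3 and N − 4 degrees of freedom. With ρ = 0:

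| N analysed | λ = 0.1225 × N × 2 | Power |
|---|---|---|
| 48 | 11.76 | 0.794 |
| 49 | 12.005 | 0.804 |
| 51 | 12.495 | 0.823 |
| 52 | 12.74 | 0.831 |

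The smallest N reaching 0.80 is 49. Rounded up to four equal groups this is 52, the protocol's figure. So ρ = 0 reproduces 52, which does not prove that the authors used it.

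**Step 2. Reproduce 60.**
- Multiplying: 52 × (1 + 0.15) = 59.8, which rounds up to 60.
- Dividing by the retained fraction: 52 / (1 − 0.15) = 61.2, so 62. With four equal groups, 13 / 0.85 = 15.3, so 16 per group and 64 in total.

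The target of 60 matches the first line and not the second. As no formula is printed, the cause remains an inference.

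**Step 3. Apply the stated loss to the stated target.**
- Overall: 60 × 0.85 = 51, against 52.
- Per group: 15 × 0.85 = 12.75, against 52 / 4 = 13.
- Loss that 60 can absorb: 60 − 52 = 8, and 8 / 60 = 13.3%.

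**Step 4. Consequence for power.** At ρ = 0, going from 52 to 51 lowers interaction power from 0.831 to 0.823, about 0.9 percentage points. Expected completers (51) still exceed by two the 49 at which 0.80 is reached. At a positive correlation the interaction power is higher: with 51 analysed it is 0.94 at an assumed ρ = 0.3 and 0.99 at an assumed ρ = 0.5.

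**The case against.** The strongest reply is that people are whole. Fifteen per cent of 15 is 2.25; if that means two lost per group, 13 remain in each and 4 × 13 = 52. This does not rescue the statement. Losing 2 of 15 is 13.3%, whereas the protocol says 15% both overall and within each group, and at 15% the overall figure is exactly 51 with no rounding involved. The reply does show how small the gap is, and it offers another route to 60 (13 completers plus 2 losses per group). That is a reason to call multiplication by 1.15 consistent with the text and not established by it.

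A second reply is that nothing follows for the design, since the planned power is still met. This stands, and it sets the severity.

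Two stronger readings are tempting. A reader might infer that the trial is underpowered, or that it must recruit 62 or 64. The figures do not support this: under the setting that reproduces 52, power at 51 is above 0.80. A reader might also infer that the single power of 0.80 fails for the group main effect, because its power falls as the pre-post correlation rises. That depends on correlations the text does not give, and the test and correlation may be in Figure 10. At a correlation of 0, the group effect and the interaction have the same power of 0.83 at 52. No error is shown there.

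Finally, section 3.8 restricts the analysis: "Only data from participants who adhere to at least 80% of the prescribed training program will be included in the analysis". Section 3.6 does not say whether the 15% includes these exclusions. If it does not, the analysed number could fall further, but the documents do not settle this and it is not part of the inconsistency.

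**Conclusion.** The point holds as a minor arithmetic inconsistency. By section 3.6's own figures, 60 recruited with 15% loss gives 51, one below the stated 52 (12.75 against 13 per group). This needs no outside assumption beyond reading the 15% as a share of those recruited, which is the natural meaning. The statement that the effect is small rests on assumptions: the G*Power default convention, f = 0.35, and a correlation of 0, chosen because it reproduces 52. On those terms planned power is kept with a margin of two participants.

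**What to change.** Reword section 3.6; do not enrol more participants. Either of two statements would make the figures agree:

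- 60 recruited with 15% loss leaves about 51 analysed, 12 to 13 per group; or
- 60 recruited allows for about 13% loss (8 of 60) while keeping 52.

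If the first is used, restate the power at 51 from the authors' own G*Power inputs, including the correlation entered, and not from the value of 0 assumed here. In either case name the effect to which the power refers. The group-by-time interaction is the natural one, since section 1.4.2 sets out "to compare the differential effects of different training modes on stability improvement".

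The cost is one or two sentences and one rerun of the existing G*Power calculation. Recruitment, allocation and analysis do not change.

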### 3.7 SAMPLING METHOD AND SUBJECT RECRUITMENT

We will use convenience sampling to recruit participants, ensuring that all participants are female beginner gymnasts meeting the inclusion criteria. Recruitment will be conducted with prior approval from the Gymnastics Teaching and Research Department of Beijing Sport University. Additionally, recruitment posters will be displayed on the first-floor bulletin board of the university's teaching building. Eligible participants will be contacted via WeChat to confirm their interest in joining the study. Group allocation will be conducted using a random number table. All participant information will remain strictly confidential unless required by law.

### **3.8 INTERVENTION METHODS**

Participants in the SG intervention group will complete an 8-week training program consisting of Plank Support, Single-Leg Stance, Eyes-Closed Double-Leg Stance, and Half-Squat Exercise. The DG intervention group will engage in Landing Control Training, Balance Beam Walking, jumping onto the Balance Beam, and Squat-to-Stand Exercises. The SDG intervention group will perform Plank Support, Single-Leg Stance, Eyes-Closed Double-Leg Stance, Half-Squat Exercise, Landing Control Training, Balance Beam Walking, jumping onto the Balance Beam, and Squat-to-Stand Exercises. Each exercise will be repeated 3 times or the corresponding number of times per session, with each session lasting 15 minutes (including 30 minutes of dynamic and static balance exercises), conducted twice a week for 8 weeks. All participants will enroll simultaneously, and each group will be guided by qualified instructors. Before and after each training session, participants will wear a heart rate monitor (Xiaomi Smart Band) on their wrist to ensure adherence to the prescribed training intensity outlined in Tables 13, 14, and 15. Additionally, participants may adjust their limb positions and movement intensity based on their physical condition. At the end of each session, training logs will be completed to document the activities. Only data from participants who adhere to at least 80% of the prescribed training program will be included in the analysis.

Participants in the control group (CG) will continue their regular training routine as detailed in Tables 7 and 8. They will be advised to maintain their usual daily activities without incorporating any additional exercises.

Table 13: Static balance training intervention content (n=15)

Week	content	Minutes/ Groups	Inter-group Rest Duration	Training duration	HR Monitoring Indicators	Heart Rate Monitoring Equipment	Intervention time	Heart rate range	Equipment
W 1	baseline test								
W 2-3	①Double leg stand ②Single leg stand	1/3	Rest for 2 minutes	15minutes	Resting Heart Rate (Before Training)/Maxi mum Heart Rate/Maximum Heart Rate	Xiaomi Smart Band	8 weeks, 2 times per week, 15 minutes each time	80bpm-100bpm	Balance board、BOSU ball
W 4	①Eyes-closed double-leg stance ②Plank support	1/3	Rest for 2 minutes	15minutes				80bpm-110bpm	Balance board 、 BOSU ball、 Gymnastic mat
W 5	①Eyes-closed Single-leg stance ②Half Squat Exercise	1/3	Rest for 2 minutes	15minutes				80bpm-110bpm	Gymnastic mat、 Balance board、 BOSU ball
W 6	①Jumping onto BOSU ball + Eyes-closed double-leg stance ②Single-Leg Standing Leg + Leg Lift Exercise	1/3	Rest for 2 minutes	15minutes				80bpm-120bpm	Balance board、BOSU ball
W 7	①Single-Leg Standing Leg + Leg Lift Exercise ② Single-Leg Standing Pointe Exercise	1/3	Rest for 2 minutes	15minutes				80bpm-120bpm	Gymnastics ball、balance board、 BOSU ball
W 8	Post test								

Table 14: Dynamic balance training intervention content (n=15)

Week	content	Times/ Groups	Inter-group Rest Duration	Training duration	HR Monitoring Indicators	Heart Rate Monitoring Equipment	Intervention time	Heart rate range	Equipment
W 1	baseline test								
W 2-3	①Jump in multiple directions on one leg ② Half squat exercise	8/3	Rest for 2 minutes	15 minutes	Resting Heart Rate (Before Training)/Maximum Heart Rate/Maximum Heart Rate	Xiaomi Smart Band	8 weeks, 2 times per week, 15 minutes each time	90bpm-110bpm	Gymnastic mat 、 Balance beam
W 4	①Jumping onto a low balance beam ②Half squat exercise	8/3	Rest for 2 minutes	15 minutes				90bpm-110bpm	Balance beam 、 Balance board 、 BOSU ball
W 5	①Jumping onto BOSU ball ② Half squat-to-stand and catch-and-throw ball exercise	8/3	Rest for 2 minutes	15 minutes				90bpm-120bpm	Balance board 、 BOSU ball
W 6	①Practice of jumping with rotation ②Plank and convert to two-hand support	8/3	Rest for 2 minutes	15 minutes				90bpm-120bpm	Gymnastics ball 、 balance board、BOSU ball
W7	①Walking on the Balance Beam ②Landing control training	5/3	Rest for 2 minutes	15 minutes				90bpm-120bpm	Gymnastic mat 、 Balance beam
W 8	Post test								

Table 15: The combination of static and dynamic balance training content (n=15)

Week	content	Times/ Minutes	Groups	Inter-group Rest Duration	Training duration	HR Monitoring Indicators	Heart Rate Monitoring Equipment	Intervention time	Heart rate range	Equipment
W 1	baseline test									
W 2-3	①Single-leg stance+ Leg - lifting exercise ②Half squat exercise + Throwing - catching ball exercise	2min 10times	3	Rest for 2 minutes	30 minutes	Resting Heart Rate (Before Training)/Maximum Heart Rate/Maximum Heart Rate	Xiaomi Smart Band	8 weeks, 2 times per week, 15 minutes each time	90bpm-110bpm	Gymnastic mat, Balance beam
W 4	①Jumping onto a low balance beam + Walking on the Balance Beam + Landing control training ②Half Squat Exercise + Throwing - catching ball exercise	10times 10times	3	Rest for 2 minutes	30 minutes				90bpm-110bpm	Balance beam、Balance board、BOSU ball
W 5	①Jumping onto BOSU ball + Double-leg stance ②Plank and convert to two-hand support	10times (1minutes) 10times	3	Rest for 2 minutes	30 minutes				90bpm-120bpm	Balance board、BOSU ball
W 6	①Jump training + Jumping with rotation ②Plank and convert to two-hand support + Plank support	10times 10times (1minutes)	3	Rest for 2 minutes	30 minutes				90bpm-120bpm	Gymnastics ball 、balance board、BOSU ball
W 7	①Jumping onto a low balance beam + Walking on the Balance Beam + Landing control training ②Forward roll + swallow balance	10times 10times	3	Rest for 2 minutes	30 minutes				90bpm-120bpm	Gymnastic mat, Balance beam
W 8	Post test									

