### 3.2 Research design

This study employs a four-arm parallel-group randomized controlled trial design to evaluate the efficacy of static, dynamic, and combined balance training on beginner gymnasts' stability and rotational performance. Figure 2 illustrates the experimental flow, including recruitment, randomization, interventions, and outcome assessments.

[figure not shown]

Figure 2 Flow chart of the experimental design

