### **3.2.1.2 Tests and Training Plan Schedule for the Experimental Group**

The test protocols and training components for stability and jumping skills were derived from outcome measures in an unpublished systematic review and deemed appropriate following discussions with [name], a gymnastics coach at Beijing Sport University. Thus, Table 9 and 10 present the stability and jumping test programme to be conducted, table 11 outlines the 8-week training schedule for the experimental group participants.

Table 9: Stability and Jumping Test Programme

Test items	Testing time	Testing content	Testing Instruments
Stability test	Baseline Measurement End of experiment week 8 test	8 Point Star Offset	Star Excursion Balance Test
Jumping test	Baseline Measurement End of experiment week 8 test	1. Countermovement Jump 2. Single-leg countermovement Jump	Force Plate

Table 10: Gymnastic Performance Movements

Test items	Testing time	Testing content	Testing Instruments
Standing Single-leg 360 ° turn	Baseline Measurement End of experiment week 8 test	Standing Single-leg 360 ° turn	3D motion capture technology
Straight jump 360 ° turn	Baseline Measurement End of experiment week 8 test	Straight jump 360 ° turn	3D motion capture technology

[figure not shown]
Table 11: Experimental Training group

Training Programme	Routine Training	Group1 (Static balance training)	Group2 (Dynamic balance training)	Group3 (Static and Dynamic balance training)
Week 1				
baseline test				
Week 2-3				
•Activity/Mode		Basic Adaptation Period		
•Duration	• 90 minutes/per session	•15 minutes/ session	•15 minutes/ session	•30 minutes/ session
•Intensity (Heart rate)	• 100bpm-160bpm	• 80bpm-100bpm	• 90bpm-110bpm	• 90bpm-110bpm
•Inter-group Rest Duration	• 2 minutes	• 2 minutes	• 2 minutes	• 2 minutes
Week 4				
•Activity/Mode	The same content	①Eyes-closed double-leg stance ②Plank support	①Jumping onto a low balance beam ②Half squat exercise	①Jumping onto a low balance beam + Walking on the Balance Beam + Landing control training ②Half Squat Exercise + Throwing - catching ball exercise
•Duration	• 90 minutes/per session	•15 minutes/ session	•15 minutes/ session	•30 minutes/ session
•Intensity (Heart rate)	• 100bpm-160bpm	• 80bpm-110bpm	• 90bpm-110bpm	• 90bpm-110bpm
•Inter-group Rest Duration	• 2 minutes	• 2 minutes	• 2 minutes	• 2 minutes
Week 5				

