### **3.5.3 Withdrawal Criteria**

Participation in this study is entirely voluntary. Participants may refuse to participate in this study or stop participating in this study at any time without penalty or loss of benefits to which they are otherwise entitled. An example of this would be if a subject develops an illness during the intervention. The research team may also stop their participation without their consent if they breach the study eligibility criteria in any way.

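### The protocol analyses only participants with at least 80% adherence, so the groups compared are not the groups randomised, and the 80% has no consistent denominator

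*Protocol*

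**What the plan says.** Section 3.2 of the protocol sets the design: "This study employs a four-arm parallel-group randomized controlled trial design". Sections 3.6 and 3.7 allocate 15 participants to each arm with a random number table.

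Section 3.8 then fixes who is analysed: "Only data from participants who adhere to at least 80% of the prescribed training program will be included in the analysis". The list of exclusion criteria in 3.5.2 uses the same cut: "Participants with poor compliance (< 80%) who are unable to complete the 8 - week exercise intervention program". Section 3.5.3 adds: "The research team may also stop their participation without their consent if they breach the study eligibility criteria in any way". The data analysis section (3.8.3) names no analysis set, and no all-randomised analysis appears elsewhere in the readable text.

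For the control arm, section 3.8 says: "Participants in the control group (CG) will continue their regular training routine as detailed in Tables 7 and 8". It does not say whether or how the 80% applies to that routine.

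On programme length, section 3.8 has sessions "conducted twice a week for 8 weeks", Tables 13 to 15 carry the entry "8 weeks, 2 times per week, 15 minutes each time", and section 3.2.1.2 says "table 11 outlines the 8-week training schedule for the experimental group participants". The rows of Tables 11 and 13 to 15 put the baseline test in week 1 and the post-test in week 8, with training in weeks 2 to 7.

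**The concern.** Randomisation makes the arms comparable at allocation. Adherence comes afterwards and can depend on the arm, on motivation, and on how well the training is tolerated. Once participants are removed for low adherence, a difference between arms may reflect who kept attending as well as what the training did. This is a rule the protocol lays down, not a detail left for a statistical analysis plan; a plan that analysed everyone would contradict it.

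There are reasons in the protocol to expect unequal selection:

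- Only the trained arms have a balance programme to adhere to.
- In the table rows, sessions last 30 minutes in the combined arm and 15 in the other two. The comparison between training types, which is the centre of the research questions, is therefore exposed as well.
- Section 5.4.1 expects muscle fatigue, dizziness or instability and has participants stop and rest. On a 12-session schedule, missing three sessions is enough to be dropped from the analysis, so poor tolerance can become a reason for exclusion.

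Placing the cut among the exclusion criteria does not help, because it cannot be judged at enrolment. Read with 3.5.3, it could also become a ground for removing someone before the week-8 test, and that loss could not be repaired at analysis.

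**Working it through.** **1. Sessions behind the 80%**

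Inputs: two sessions a week and 8 weeks (section 3.8, Tables 13 to 15); training in weeks 2 to 7 (rows of Tables 11 and 13 to 15).

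| Reading | Sessions | 80% of sessions | Sessions needed | Share reached by attending all 12 |
|---|---|---|---|---|
| Text and table entry | 8 × 2 = 16 | 12.8 | 13 | 12/16 = 75% |
| Table rows | 6 × 2 = 12 | 9.6 | 10 | 12/12 = 100% |

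On the first reading nobody in a trained arm can qualify. On the second, 9 of 12 (75%) fails and 10 of 12 (83.3%) passes.

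**2. Possible shift in the training-versus-control difference**

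The protocol gives neither a non-adherence rate nor a relation between adherence and outcome, so this is an illustration on assumed inputs:

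- the lowest-adhering fraction p is removed from the trained arms, and controls are not filtered;
- adherence is roughly normal, with correlation r to the change score, r from 0 to 0.5;
- p is 15% (the dropout figure in 3.6, borrowed only as a starting point), 20% or 30%.

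The mean change among those kept then moves by r × φ(q_p)/(1 − p) SD of the change score, where q_p is the p-quantile of the standard normal and φ its density.

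| p | φ(q_p)/(1 − p) | r = 0 | r = 0.3 | r = 0.5 |
|---|---|---|---|---|
| 15% | 0.274 | 0 | 0.082 | 0.137 |
| 20% | 0.350 | 0 | 0.105 | 0.175 |
| 30% | 0.497 | 0 | 0.149 | 0.248 |

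If controls also lose their lowest 10% (factor 0.195, so 0.5 × 0.195 = 0.097 at r = 0.5), the net shifts at r = 0.5 are:

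- p = 15%: 0.137 − 0.097 = 0.04
- p = 20%: 0.175 − 0.097 = 0.08
- p = 30%: 0.248 − 0.097 = 0.15

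With the same selection in every arm the shift is 0.

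Because arms of 15 are small, the result was also simulated (200,000 arms). For r = 0, 0.3 and 0.5, removing the lowest 3 of 15 gives shifts of 0, 0.10 and 0.16; removing 4 of 15 gives 0, 0.13 and 0.21.

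**3. Numbers analysed (secondary)**

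Section 3.6 raises 52 to 60: 52 × 1.15 = 59.8. After 15% dropout, 60 × 0.85 = 51 remain, or 12.75 per arm. If that allowance covers dropout alone, the 80% rule removes more. Assuming that 10% of the 38.25 remaining trained participants fall below the cut, 12.75 + 38.25 × 0.90 = 47.2 are analysed; at 20%, 12.75 + 38.25 × 0.80 = 43.4.

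**The case against.** The strongest reply is that adherence may be high. Participants take the gymnastics class as part of their degree, instructors supervise the sessions, and the balance sessions are short and only twice weekly. Routine classes record attendance, so an 80% rule could be applied to controls too. If few fall below the cut, or if selection is the same in all arms, the bias is small or nil. That is correct, and it is why the size is given as a range starting at 0. It does not rescue the rule: adherence cannot be known now, and the protocol neither applies the rule to controls nor justifies the equal loss it assumes in 3.6.

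Second, the SD figures rest on assumptions. Adherence is really a count capped at 12, so the range is not a bound, and it covers training versus control only, not contrasts between training types. This stands; the defect does not depend on those figures.

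Third, Figure 2 and the opening of section 3.2.1 could not be read in the copy available, so the statement that no other set is named is limited to the readable text. That limit also stands. Even so, the word only in section 3.8 leaves no room for a wider set.

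Fourth, the 12 scheduled sessions are the natural reference, and the 16-session reading defeats itself. That may be what was meant, but the protocol states both and has to settle it.

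**Conclusion.** The concern holds and needs correction before the trial starts. Followed as written, the protocol conditions every outcome comparison on behaviour after randomisation. The analysed arms equal the randomised arms only if nobody falls below 80%.

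The threshold conflict is a matter of arithmetic from the protocol: 10 of 12 sessions, or 13 of 16 when only 12 are scheduled.

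The bias itself cannot be sized from the protocol. Under the assumptions above it runs from 0 to about 0.25 SD of the change score. It favours training over control if exclusions fall mainly on the trained arms and adherence goes with larger gains. Equal selection in all arms makes it 0.

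**What to change.** - Make the main analysis all randomised participants in their assigned arm, whatever their attendance, and replace the sentence in section 3.8 accordingly.
- Take criterion 3 out of section 3.5.2, and make clear in 3.5.3 that low attendance does not by itself remove a participant from the study's testing or analysis. The medical and safety provisions of section 5.4.1 are unaffected.
- Seek the planned week-8 test from every willing participant and report missing tests by arm. The repeated-measures ANOVA of Tables 16 to 20, as usually run, drops anyone without both tests. A likelihood-based mixed model for both time points, with its missing-at-random assumption stated, is one way to keep those with a baseline only.
- Keep the 80% set as a labelled sensitivity analysis, stating its denominator and how it applies to controls.
- Reconcile the 8-week statements with the weeks 2 to 7 rows, and the 15-minute entry in Table 15 with its 30-minute rows.

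The cost is mainly wording. Testing low attenders concerns about 7 to 14 of the 45 trained participants under the assumed 15% to 30% (45 × 0.15 = 6.75; 45 × 0.30 = 13.5), using tests already planned; some who leave altogether may not be testable. The estimated effect will be somewhat diluted by poor attenders, and the sensitivity analysis keeps the adherence question visible. Table 22 dates recruitment to 1/7/2026 and the protocol is dated 25/9/25, so on that timetable the change can precede enrolment.
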